- Altered state of consciousness (first sleep stage)
- Mouth breathing and loss of lingual-palatal and labial-labial contact
- Passive craniocervical flexion

Facilitating parameters:

- Cephalocervical extension
- Mandibular advancement
- Tongue protraction
- Efficient nasal ventilation

These considerations allow us to establish an examination protocol to attempt to answer the following questions:

- Can the subject consciously perceive variations in airflow/or intraluminal pressure in the upper airways caused by the various aggravating and facilitating parameters?
- Can the sensations of ventilatory flow/intraluminal pressure felt by the subject constitute a complementary tool for screening for obstructive sleep disorders?

The goal of the clinical examination is to cause instability of the oropharyngeal mechanics. This instability can cause a modification of the pharyngeal lumen and a modification of the resistance of the VAS to the pressure linked to the ventilatory flow. These will lead to a modification of the inspiratory pressure gradient and stimulate the mechanoreceptors located in the VAS. The responses to a questionnaire by subjects who present sleep disorders exposed to these variations in resistance (aggravating or facilitating) on their subjective feeling allows the establishment of a perception scale which, compared to a control group without sleep disorders, will determine if the sensitivity of the inputs is comparable between the groups and if a tool for screening sensory inputs is possible.

Protocol:

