The questionnaires to assess patients' pharyngeal ventilatory perceptual potential/the quality of spontaneous nasopharyngeal perception during ventilation are administered when patients come to the consultation to request the results of the pharyngeal ventilatory perceptual analysis. The examiners are blinded, unaware of the results. Patients are randomly assigned according to their order of arrival. The first questionnaire consists of 7 items selected to aggravate or facilitate upper airways permeability (supine position, modified state of consciousness with muscle relaxation, tongue posture, cephalic flexion, cephalic extension, mandibular protraction, nostrils aperture). This first questionnaire try to evaluate if all subjects are able to feel aggravating or facilitating factors by on/off answers. The second questionnaire consists of 18 items related to upper airway collapsibility. Each item concerns the aggravating or facilitating factors perceived by the patient or the therapist with clinical maneuvers, factors known to be unfavourable to the permeability of the upper airways (snoring, oral ventilation, tonsils, dento-skeletal class, etc.), as well as two questionnaires used in the sleep laboratory of the André Renard clinic (Epworth Sleepiness Scale and FFF questionnaire).

[figure not shown]
For each of these items, the patient's or practitioner's response will be noted.

Performing the examination:

- Sensory-motor awareness of nasal and pharyngeal breathing (patient in a seated position): explain to the patient what to observe and feel and where (soft palate, tonsils, vibration during snoring, etc.)
- Read the questionnaire to the patient: it must be understood
- Ask the patient to answer each item and record the response.

The examination lasts approximately 20 minutes.

This examination requires patient involvement but carries no risks or side effects.

STATISTICAL ANALYSIS PLAN

(translation of the Statistical analysis report download in SAP section from an independent Biostatistician: [name], MyStat.be)

Software used for analysis: R version 4.4.1(R Core Team (2024). R: A language and environment for statistical computing. R Foundation for Statistical Computing, Vienna, Austria. URL <https://www.R-project.org/>) and Microsoft Excel for manipulating and preparing the data tables. data files used and appended: d1_final.csv, d2_final.csv

1 - d1_final.csv: sensitivity parameters taken from 112 patients

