2 - d2_final.csv: parameters taken from 101 patients (excluding CHR patients considered normal after polysomnography)

Discrete variables for classification into groups :

- STATUS3: 2 categories: healthy patients (= non-CHR control patients and normal CHR patients) and pathological patients (= CHR patients affected to varying degrees)
- STATUS4: 4 categories: control patients (= non CHR), normal patients (= CHR N), mild symptom patients (= CHR SL), moderate symptom patients (= CHR SM) and severe symptom patients (= CHR SS).

A. Descriptive statistics (based on file n°1 - sensitivity)

B. Descriptive statistics (based on file n° 2 - predictive score)

C. Normality tests for intermediate and final scores

- Parameter ST1 (SubTotal1) = aggravating parameters

Shapiro-Wilk normality test

- Parameter ST2 (SubTotal2) = facilitating parameters

Shapiro-Wilk normality test

- Parameter ST1+ST2 (SubTotal1+ SubTotal2) = subjective sensitivity of patients

Shapiro-Wilk normality test

- Parameter ISF (Intermediate Final Score) = subjective sensitivity of patients and practitioner

Shapiro-Wilk normality test

- Parameter TFS (Total Final Score) = subjective sensitivity of patients and practitioner + valuable factors

Shapiro-Wilk normality test

D. Spearman correlation tests between final scores and certain variables

E. Non-parametric tests on patient sensitivity :

Given the non-normal distribution of the various variables other than IFS and TFS, non-parametric tests (based on the median of the data) were applied to analyse the differences between the groups (according to the STATUS3 and STATUS4 classification criteria). To analyse any differences in sensitivity between patient groups, Kruskal-Wallis tests were applied. In this type of analysis, having a p-value greater than 1% and ideally greater than 5% would indicate the absence of differences between groups.

Then, to see if the median of a particular group is different from 0 (= no sensitivity: not feeling the differences in airflow induced by the different tests given by the operator), Wilcoxon tests were performed on each group of data. If the p-value is small (less than 5%, ideally less than 1%), the null hypothesis that the score is identical to 0 is rejected. In this case, it means that the patients in the test group feel the differences in airflow depending on their position. This is the case for all the patient groups tested on ST1, ST2 and ST1+ST2.

[figure not shown]

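### Section E tests only pooled subtotals against zero, so its conclusion that patients feel airflow differences by position is not supported manoeuvre by manoeuvre

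*Combined protocol and SAP*

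**What the plan says.** The protocol's first question is whether a subject can consciously perceive variations in airflow or pressure "caused by the various aggravating and facilitating parameters". The first questionnaire is built for this. It takes on/off answers on seven manoeuvres: "supine position, modified state of consciousness with muscle relaxation, tongue posture, cephalic flexion, cephalic extension, mandibular protraction, nostrils aperture". Under the heading on performing the examination, the answer to each item is to be recorded.

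The analysis works on sums. SAP Section C defines "Parameter ST1 (SubTotal1) = aggravating parameters", defines ST2 in the same way for the facilitating parameters, and treats ST1+ST2 as the patient's subjective sensitivity. Section E then states that "Wilcoxon tests were performed on each group of data", with zero taken to mean "not feeling the differences in airflow induced by the different tests given by the operator". The decision rule is: "If the p-value is small (less than 5%, ideally less than 1%), the null hypothesis that the score is identical to 0 is rejected". Rejection is read as: "it means that the patients in the test group feel the differences in airflow depending on their position". The reported result is: "This is the case for all the patient groups tested on ST1, ST2 and ST1+ST2".

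The readable text describes no test or interval for a single manoeuvre. Section A announces descriptive statistics on the sensitivity file without saying whether they are per item.

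**The concern.** The question and the form work by manoeuvre, the test works by subtotal, and the conclusion returns to positions. The last step does not follow. On the on/off form, a subtotal above 0 says only that at least one of its items was scored. A significant result would look the same if patients felt every manoeuvre in the subtotal or only one of them.

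The rule is also weak as evidence about a group. With scores that cannot fall below zero, every non-zero value lies on the same side, so a handful of patients is enough to reject. In the larger groups, rejection does not even show that most patients felt something, although Section E presents the test as one about the group's median.

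At stake is the answer to one of the study's two stated questions. A reader would take Section E as evidence for each manoeuvre when it is evidence only for a pooled score.

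**Working it through.** **Is there a figure to reproduce?** No. The readable text gives no p-value or subtotal for Section E, so the check is on the rule itself.

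**Inputs**
- Thresholds: 5%, ideally 1% (Section E). Sidedness is not stated; two-sided is assumed.
- Scoring: each item of the first questionnaire is 0 or 1; no item on either form is negative.
- Group sizes: 60 controls; 9 mild, 18 moderate and 14 severe (group descriptions after the forms). The sensitivity file has 112 patients and the score file 101, so CHR-normal = 112 − 101 = 11. Check: 9 + 18 + 14 = 41; 60 + 41 = 101; 101 + 11 = 112.

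**Step 1: how many patients are needed to reject.** In a one-sample Wilcoxon signed-rank test against 0 with zeros dropped, if m patients score above zero all signed ranks are positive, and the exact two-sided p is 2 × 0.5^m.
- m = 5: 0.0625
- m = 6: 0.031
- m = 7: 0.016
- m = 8: 0.0078

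Six patients suffice at 5% and eight at 1%. With the tie-corrected normal approximation and continuity correction (all non-zero scores equal), five suffice at 5% (p = 0.037).

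Six patients as a share of each group:
- controls 6/60 = 10%
- moderate 6/18 = 33%
- severe 6/14 = 43%
- CHR-normal 6/11 = 55%
- mild 6/9 = 67%

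With 6 of 60 controls above zero, the other 54 score 0 and the sample median is 0, yet the test rejects.

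**Step 2: one manoeuvre carrying a subtotal.** Suppose every patient feels the supine change and no other aggravating manoeuvre, so that ST1 = 1 for all. Exact p = 2 × 0.5^9 = 0.0039 in the smallest group and 2 × 0.5^60 = 1.7 × 10^-18 in controls. Section E's conclusion on ST1 would stand, with relaxation and flexion felt by nobody.

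**Step 3: a less extreme case.** Let one manoeuvre be felt by a share p of patients (assumed) and the rest of its subtotal by nobody. The chance of significance in a group is P(X ≥ 6), X ~ Binomial(n, p). At p = 0.8:

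| Group | n | Chance at 5%, exact |
|---|---|---|
| Control | 60 | 1.00 |
| CHR-normal | 11 | 0.99 |
| Mild | 9 | 0.91 |
| Moderate | 18 | 1.00 |
| Severe | 14 | 1.00 |

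Multiplied together, all five groups are significant with probability 0.90. For p = 0.5, 0.7, 0.8 and 0.9 the figure is 0.10, 0.67, 0.90 and 0.99 (exact), or 0.33, 0.88, 0.98 and 1.00 (normal approximation, threshold five).

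**Step 4: what item-level intervals would show.** For 0 of n, the exact 95% upper bound is 1 − 0.025^(1/n): 6.0% (n = 60), 18.5% (18), 23.2% (14), 28.5% (11), 33.6% (9). An unfelt manoeuvre would be visible as such, with its uncertainty stated.

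**Step 5: which items are in ST1 and ST2.** The SAP does not list them. The 112-patient sensitivity file suggests the seven-item form. The definitions in Section C also fit the 18-item form: items 1–3 (maximum 1 + 1 + 2 = 4), items 4–6 (2 + 2 + 2 = 6) and therapist items 7–8 (2 + 1 = 3) sum to the printed Intermediate Final Score maximum of 13. On that reading, item 5 is a measured range of movement that adds up to 2 points to ST2 with no sensation reported, while flexion or extension felt only at the end of the range scores 0. A score above 0 then need not mean felt, and 0 need not mean not felt.

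**The case against.** The strongest reply is that Section E never claims every manoeuvre is felt. The protocol describes the first questionnaire as checking whether subjects can feel aggravating or facilitating factors, and ST1 and ST2 follow those two classes. They are tested separately, so one manoeuvre cannot carry both subtotals unless it is counted in both; the tongue item, labelled as either aggravation or facilitation, is the only candidate. This stands, and it limits the point: one felt manoeuvre carries its own subtotal and ST1+ST2. It does not rescue wording that speaks of differences by position on the strength of a sum.

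A second reply is that item frequencies may be in Section A or in the figure not shown. That is possible, so the point is confined to the inference as written: the variables named are pooled and the conclusion is not.

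Third, the scenarios are hypothetical. They are; they show what the rule cannot detect, not what happened.

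A reader might go further and infer that the study cannot say which manoeuvres are perceived. The documents do not support this, because each answer is recorded. Nor do they support saying that the 18-item form drops tongue posture and nasal patency with no item-level support. Items 9 and 10 retain low tongue posture and habitual nasal difficulty, though not as felt-change manoeuvres, and item-level results may lie in material not shown.

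**Conclusion.** The concern holds, limited to the inference. Rejecting zero for ST1, ST2 or ST1+ST2 supports only a statement about that pooled score. About six patients above zero in a group produce it, whichever item they scored on. That is one control in ten, but two thirds of the mild group, so the weakness is greatest in the larger groups.

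This rests on a two-sided signed-rank test with zeros dropped, on non-negative scores (clear from both forms), and on the readable text of Section E. The probabilities in Step 3 depend on assumed perception rates.

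It would be wrong to infer that some manoeuvre was in fact unfelt: nothing in the documents shows that. The uncertainty over which form feeds the subtotals does not remove the concern; under the 18-item form, the link from score to perception is weaker still. This is a modest but worthwhile correction, since it bears on one of two stated questions and needs no new data.

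**What to change.** 1. State in the SAP which form and which items make up ST1 and ST2, including where the tongue item is counted.
2. Answer the first question with one table: for each of the seven on/off items, the number and proportion answering 1, with an exact (Clopper-Pearson) 95% confidence interval, in each STATUS4 group. Include it as the inferential basis for Section E even if Section A already lists frequencies. With 7 items and five groups there are 35 intervals; say that they are not simultaneous.
3. Word the Section E conclusion manoeuvre by manoeuvre from that table.
4. Keep ST1, ST2 and ST1+ST2 as summaries, and limit any statement from their Wilcoxon tests to the pooled score.

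The cost is one table from answers already recorded and a few changed sentences. The drawback is wide intervals in the small groups: none of 9 mild patients feeling a manoeuvre would still be compatible with a true rate of up to 33.6%.

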F. Parametric tests on the prediction of patients' pathological status (SFI and SFT scores):

For these analyses, as the IFS and TFS scores follow a normal distribution, ANOVAs (analyses of variance) were performed. For discrete variables with more than 2 levels of value (STATUS4), a post-hoc 2-to-2 comparison analysis was performed (Tukey) to see which level of the variable differed from one another. Significant values are highlighted in bold red.

[figure not shown]
G. Determination of cut-off values for IFS and TFS:

[figure not shown]
The Cutoff_final txt file includes the various sensitivity and specificity calculations as well as the Youden index in order to determine the best cut-off value (largest Youden). The ROC curves allow the values in the file to be appreciated graphically.

Upper rhino-oro-pharyngeal airway permeability - Subjective neuro-sensory evaluation

Assessment of oro-pharyngeal sensitivity				
Date :	Name:			age:
Tests	Items			Score 1 0
	Aggravation or facilitation felt = 1 No aggravation or no facilitation felt = 0			
Aggravation maneuver	1	Supine position		
Aggravation maneuver	2	Modified state of consciousness (overall relaxation)		
Aggravation maneuver	3	Cephalic Flexion		
Aggravation or Facilitation maneuver	4	Upper-anterior tongue to lower tongue (= aggravation) or lower tongue to upper-anterior tongue (= facilitation)		
Facilitation maneuver	5	Cephalic Extension		
Facilitation maneuver	6	Mandibular protrusion		
Facilitation maneuver	7	Nostrils aperture		
Total Score				... / 7
Comments :				
www.osteovox.be				

Upper rhino-oro-pharyngeal airway permeability - Subjective neuro-sensory evaluation						
Date :	Name :			age: IMC:		
Tests	Items			Scores		
	0	0,5	1	2		
Aggravation maneuver	1	Supine position: aggravation=1 / no aggravation= 0				
Aggravation maneuver	2	Modified state of consciousness (overall relaxation) aggravation=1 / no aggravation= 0				

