subjective perception of nocturnal breathing patterns	13	At night, you breathe mainly: through the mouth=2 / mixed nose-mouth=1 / through the nose =0				
Therapist observation	14	Dento-skeletal class: class I or III = 0 / class II = 1				
Therapist observation: Tonsils: grades 0-1-2 =0 / grades 3-4 =1	15	Quote : 				
Therapist observation: Mallampati: grade 1-2 =0 / grade 3-4 =1	16	Quote : 				
Epworth Sleepiness Scale	17	score: ≤ 8 =0 / $9\text{--}>14$ =1 / ≥ 15 =2				
FFF questionnaire	18	score ≤ 10 =0 / ≥ 11 =1				
Final Total Score (FTS): low risk of OSAS ≤ 10 / high risk of OSAS ≥ 11				... / 26		
Comments :						
www.osteovox.be						

Study process adapted from the CONSORT 2010 flowchart.

STUDY GROUP: The final sample included 41 patients diagnosed with OSAH (mild= 9, moderate=18; severe= 14).

The study sample included 13 women and 28 men, with a mean age of 49.30 years, and a mean body mass index (BMI) of 30.70 kg/m².

CONTROL GROUP: The final sample included 60 patients without OSA based on subjective scales used in sleep medicine in Liège (Epworth, Berlin, Pichot, FFF).

The study sample comprised 20 men and 40 women, with a mean age of 41.76 years and a mean body mass index (BMI) of 22.78 kg/m².

Predictability of OSA with a Subjective Screening Scale

Predictive Value of OSA Based on the Evaluation of the Subjective Feeling of the Air Flow
Through Airways, a Randomized Controlled Study

Herstal, February 3, 2023

Favorable Opinion

Composition of the Ethics Committee:

- - [name] - Vascular Surgeon
- - [name] - External General Practitioner
- - [name] - Palliative Care
- - [name] - Anesthesiologist
- - [name] - Geriatrician
- - Maître [name] - Lawyer at the Liège Bar
- - [name] - Hospital Mediator
- - [name] - Psychologist
- - [name] - Social Worker
- - [name] - Hospital Pharmacist
- - [name] - Nurse in the Intensive Care Unit

Subject:

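### SAP Section F presents a comparison of group means as prediction, and Section G picks the largest-Youden cut-off with no AUC, confidence interval or optimism correction in the visible text

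*Combined protocol and SAP*

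**What the plan says.** The protocol's second question, in the list that follows the facilitating parameters, is whether perceived airflow can serve as an additional screening tool for obstructive sleep disorders. That is a question about classifying individuals.

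The SAP section that appears to address it is headed "F. Parametric tests on the prediction of patients' pathological status (SFI and SFT scores". I take SFI and SFT there to be the IFS and TFS named elsewhere in the SAP, and TFS to be the FTS on the questionnaire form. The method given is: "as the IFS and TFS scores follow a normal distribution, ANOVAs (analyses of variance) were performed". Pairwise Tukey comparisons are added for STATUS4. The only reading of the results described is: "Significant values are highlighted in bold red".

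Section G refers to a file of sensitivity, specificity and Youden values, used "in order to determine the best cut-off value (largest Youden"). Of the curves it says: "The ROC curves allow the values in the file to be appreciated graphically". No visible text in either section names an AUC, a confidence interval, a minimum accuracy or a correction for choosing the cut-off on the same data. The second questionnaire form already prints risk boundaries: 8 or more out of 13 for IFS, and 11 or more out of 26 for FTS.

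**The concern.** ANOVA asks whether group means differ. It does not say how far the two score distributions overlap, and the overlap decides whether a score can sort individual patients. With about 100 people, means can differ significantly while the distributions overlap heavily. Placing the ANOVA under a heading about prediction invites the reader to take a small p-value as evidence for screening.

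The largest Youden index has a related weakness. A maximum over many candidate cut-offs exists in every dataset, and its value in the sample that chose it is biased upwards. Without an interval or a correction, the reader cannot separate real discrimination from the effect of searching. At stake are the answer to the screening question and the credibility of the boundaries printed on the form.

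**Working it through.** The documents give no target accuracy, effect size or standard deviation, so there is no plan figure to reproduce. The check asks what a just-significant ANOVA implies for classification, and what the largest-Youden rule returns when the score carries no information.

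**Inputs from the documents**
- Cases: "The final sample included 41 patients diagnosed with OSAH (mild= 9, moderate=18; severe= 14"); 9 + 18 + 14 = 41.
- Controls: "The final sample included 60 patients without OSA based on subjective scales used in sleep medicine in Liège (Epworth, Berlin, Pichot, FFF").
- Predictive-score file: "parameters taken from 101 patients (excluding CHR patients considered normal after polysomnography"); 41 + 60 = 101, which agrees.
- Significance level: 5%, ideally 1%, written out in Section E only.

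**Assumptions:** that level carries over to Section F and is two-sided; scores are normal with equal variances; the comparison is the two-group one, for which ANOVA is equivalent to a t-test on 99 degrees of freedom.

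**1. Smallest significant difference.** d = t(0.975; 99) × √(1/41 + 1/60) = 1.984 × 0.2026 = 0.402.

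**2. What that difference means for classification.**
- AUC = Φ(d/√2) = Φ(0.284) = 0.61.
- At the midpoint cut-off, sensitivity = specificity = Φ(d/2) = Φ(0.201) = 58.0%.
- Youden = 2 × 0.580 − 1 = 0.16.
- At p = 0.01: d = 2.626 × 0.2026 = 0.532, AUC 0.65, sensitivity = specificity 60.5%, Youden 0.21.

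**3. How this changes with larger differences.**

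| d | AUC | Sensitivity = specificity |
|---|---|---|
| 0.40 | 0.61 | 58.0% |
| 0.80 | 0.71 | 65.5% |
| 1.00 | 0.76 | 69.1% |
| 1.50 | 0.86 | 77.3% |

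All four rows are significant at 5% if observed with 41 v 60, so significance alone does not tell them apart.

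**4. Largest Youden with no discrimination.** Simulation, 41 v 60, half-point scores, 8,000 runs per score, with assumed means and SDs (IFS 6.5 and 2.5; TFS 10 and 4).
- IFS: mean largest Youden 0.099, 95th percentile 0.212.
- TFS: mean 0.104, 95th percentile 0.220.
- A cut-off with positive Youden was found in 97% (IFS) and 98% (TFS) of runs.
- The two-group test was significant in only 4.7% and 5.3% of the same runs.

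**5. Optimism with weak discrimination.** With a true d of 0.402 the population Youden is 0.16. The in-sample largest Youden for TFS averaged 0.23, an overstatement of about 0.07.

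**6. Precision.** At 58%, the approximate 95% half-width is 1.96 × √(0.58 × 0.42/41) = 0.15 for sensitivity and 1.96 × √(0.58 × 0.42/60) = 0.12 for specificity. For an observed AUC of 0.80, the Hanley-McNeil standard error is 0.047, giving 0.71 to 0.89.

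**7. Group formation.** Epworth and FFF help to define the controls and are also items 17 and 18 of the FTS, worth up to 2 + 1 = 3 of its 26 points. They are not in the IFS (items 1 to 8). The CHR patients found normal on polysomnography are left out of the 101. These are referred patients without disease, plausibly the hardest to tell from cases. Both features are likely to raise the FTS AUC, and the second bears on the IFS too. The documents give no figure from which to size either effect.

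**The case against.** The strongest reply is that Section G already assesses classification. It tabulates sensitivity and specificity numerically, and the ROC curves display those numbers rather than replace them. A 58%/58% score would appear there as 58%/58%. This stands, and it limits the criticism of Section G to what is missing: a summary of discrimination, its uncertainty, and a correction for choosing the cut-off in-sample.

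A reader might infer that no result can come out negative. The documents do not support that. The ANOVA can be non-significant, as it was in about 95% of the null simulations, and a weak score would show in the Section G table. What is absent from the visible text is a stated criterion for inadequate accuracy.

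A reader might also infer that a score misclassifying about 42% of patients would count as predictive. No sentence says that a significant ANOVA establishes prediction, and none makes the cut-off depend on Section F. The link comes from a heading in a translated report. The 42% is simply 100% − 58%, the error at the edge of significance, and should not be attached to this scale.

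Finally, figures in both sections are not shown and the cut-off file is not supplied, so an AUC may have been reported there. That cannot be checked. An AUC in a figure would meet part of the request, but would not alter the heading of Section F or correct the optimism.

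**Conclusion.** The point holds as a cheap improvement to the analysis and its wording. Section F compares means and should not be read as evidence of prediction. Section G selects a cut-off without, in the visible text, an AUC, an interval or an optimism correction.

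At the boundary of 5% significance the implied accuracy is about 58% sensitivity and specificity (AUC about 0.61). This rests on the Section E level applying to F, a two-sided two-group test, and equal-variance normal scores; larger differences imply better accuracy. The null result for the largest Youden (mean about 0.10, 95th percentile about 0.21 to 0.22) rests on assumed score means and SDs. None of these figures estimates the accuracy of this scale, which the visible documents do not report.

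**What to change.** 1. Retitle Section F as a comparison of group means, and do not use its p-values as evidence of prediction.
2. In Section G, answer the screening question from the AUC of IFS and of TFS/FTS, each with a 95% CI.
3. Report sensitivity and specificity at the chosen cut-off with 95% CIs and a bootstrap optimism correction that repeats the cut-off search in every resample.
4. If the sponsor adds a minimum AUC, label it post hoc, because the SAP already reports the analysis in the past tense. The value is for the sponsor to justify.
5. State beside the FTS AUC that it is likely inflated, because Epworth and FFF both define the controls and are scored as items 17 and 18, and because polysomnography-normal CHR patients are excluded. The bootstrap does not remove either effect.

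The cost is SAP wording and a short re-analysis of the existing 101 records; no new patients are needed. The downside for the sponsor is that the accuracy figures will look less favourable and the scale may not be supported.
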